5.7.1. Restricted Medications

The following medications have restrictions on use during the treatment phase of the study:

- Aspirin in doses exceeding 81 mg/day is not permitted. Low-dose aspirin (≤ 81 mg/day) is permitted. Acetaminophen and nonsteroidal anti-inflammatory drugs (NSAIDs; eg, ibuprofen) are permitted.
- Co-administration with strong CYP3A4 inhibitors; alternative agents with less CYP3A inhibition should be considered ([Appendix B](#)). Differences in individual sensitivity and variation CYP enzyme inhibition may result in the need for dose reduction of INCB039110 and/or ibrutinib. The sponsor medical monitor may be consulted for advice when using these agents.
- Co-administration with CYP3A4 moderate/weak inducers ([Appendix B](#)).
- If concomitant administration of an anticoagulant/antiplatelet medication is indicated, then caution and enhanced monitoring is required. History of thrombocytopenia and any concurrent INCB039110-related thrombocytopenia should be a factor in the choice of anticoagulant and dose.
- Systemic corticosteroid doses greater than the equivalent of 10 mg prednisolone per day are not permitted from the screening visit through the follow-up visit, except with medical monitor approval.
- Any medications known to cause QT prolongation should be used with caution; periodic electrocardiogram (ECG) and electrolyte monitoring should be considered.
- Supplements such as fish oil and vitamin E preparations should be avoided. Ibrutinib should be used with caution in subjects requiring other anticoagulants or medications that inhibit platelet function.

- For subjects requiring the initiation of therapeutic anticoagulation therapy (eg, atrial fibrillation), the risks and benefits of continuing ibrutinib treatment should be considered. If therapeutic anticoagulation is clinically indicated, then treatment with ibrutinib should be withheld and not restarted until the subject is clinically stable and has no signs of bleeding. Subjects should be observed closely for signs and symptoms of bleeding. No dose reduction is required when study drug is restarted. Warfarin or vitamin K antagonists should not be administered concomitantly with ibrutinib.

5.7.2. Prohibited Medications and Measures

The following medications are prohibited during the treatment:

- Any concurrent anticancer therapy (eg, chemotherapy, radiation therapy, surgery, immunotherapy, biologic therapy, hormonal therapy, or tumor embolization) other than those specified in the Protocol.
- Any investigational medication before withdrawing from the study.
- Corticosteroids for the treatment of the underlying malignancy.
- Potent inducers of CYP3A4.
- Warfarin or vitamin K antagonists.

5.8. Procedural Restrictions

5.8.1. Minor Surgical Procedures

For minor procedures (eg, a central line placement, needle biopsy, thoracentesis, paracentesis), ibrutinib should be withheld for at least 3 days before the procedure and should not be restarted for at least 3 days after the procedure. For bone marrow biopsies that are performed while the subject is receiving ibrutinib, it is not necessary to withhold ibrutinib for these procedures.

5.8.2. Major Surgical Procedures

For any surgery or invasive procedure requiring sutures or staples for closure, ibrutinib should be withheld at least 7 days before the intervention until at least 7 days after the procedure. Ibrutinib should be restarted at the discretion of the investigator when the surgical site is reasonably healed without serosanguineous drainage or the need for drainage tubes.

5.8.3. Emergency Procedures

For emergency procedures, ibrutinib should be withheld after the procedure until the surgical site is reasonably healed or for at least 7 days after the urgent surgical procedure, whichever is longer.

6. STUDY ASSESSMENTS

All study assessments will be performed as indicated in the schedule of assessments in [Table 8](#); the order of assessments is suggested by the order of mention within the schedule. Laboratory assessments are shown in [Table 9](#).

Table 8: Schedule of Assessments

Procedure	Section	Screening	Treatment				EOT	Follow-Up	Comments
		Day -28 to -1	Day 1	Day 8 (± 3 days)	Day 15 (± 3 days)	Day 28/Q28D (± 3 days)		EOT + 30-35 Days	
Informed consent	7.1	X							
Contact IVRS	7.2	X	X			X	X		
Inclusion and exclusion criteria	3.1 3.2	X	X						
Demography and medical history	7.3.1	X							
Prior/concomitant medications	7.3.2	X	X	X	X	X	X	X	
Physical exam/ weight/height	7.4.2 7.4.3	X*	X	X	X	X	X	X	*Comprehensive exam at screening; targeted physical exam thereafter. Height required at screening only.
Vital signs	7.4.4	X	X	X	X	X	X	X	
12-lead ECG	7.4.5	X*	X*	X**					*Triplicate ECGs will be performed during screening and on Day 1 before starting study treatment. **Triplicate ECGs will be performed predose and 2 hours (± 15 minutes) after receiving INCB039110 on Day 8. Additional ECGs may be performed as clinically indicated.
ECOG status	7.6.1	X	X			X	X	X	
AE assessment	7.4.1	X	X	X	X	X	X	X	
CT or MRI	7.5.1	X				X*	X		*Week 8, Week 16, and then every 16 weeks ± 1 week. Also required to confirm CR.
FDG-PET scan/PET-CT	7.5.2	X				X*			*Required at baseline and to confirm CR or if clinically indicated.

Table 8: Schedule of Assessments (Continued)

Procedure	Section	Screening	Treatment				EOT	Follow-Up	Comments
		Day -28 to -1	Day 1	Day 8 (± 3 days)	Day 15 (± 3 days)	Day 28/Q28D (± 3 days)		EOT + 30-35 Days	
Bone marrow exam	7.5.3	X*							*Required as a screening assessment unless performed as per standard of care within 60 days of Day 1. Repeat to confirm CR or if clinically indicated.
Dispense study drug	5.1		X			X			
Study drug accountability	5.4		X	X	X	X	X		
INCB039110 administration	5.2.1		X*	X*	X*	X*			*Subjects should refrain from taking INCB039110 on clinic visit days until after local laboratory blood samples are collected.
Ibrutinib administration	5.3.1		X*	X*	X*	X*			*Subjects should refrain from taking ibrutinib on clinic visit days until after local laboratory blood samples are collected.

FDG = fluorodeoxyglucose; PET = positron emission tomography.

Table 9: Laboratory Assessments

Laboratory Tests	Section	Screen	Day 1	Day 8 (± 3 days)	Day 15 (± 3 days)	Day 28/Q28D (± 3 days)	EOT	Follow-Up	Details
Local Laboratory Samples									
Serum chemistries	7.4.6.1	X	X		X	X	X	X	Day 1 laboratory tests may be omitted if the screening tests occurred in preceding 7 days. All lab draws should be performed before dose administration.
Hematology	7.4.6.2	X	X	X	X	X	X	X	Day 1 laboratory tests may be omitted if the screening tests occurred in preceding 7 days. All lab draws should be performed before dose administration.
Coagulation panel	7.4.6.2	X	X			X*	X		Day 1 laboratory tests may be omitted if the screening tests occurred in preceding 7 days. All lab draws should be performed before dose administration. *After Day 28, should be repeated every 3 months, ie., Day 112, Day 196, etc.
Serology	7.4.6.5	X							
Serum pregnancy	7.4.6.4	X					X		All female subjects of childbearing potential; negative pregnancy test must be obtained within 7 days of first dose of study treatment.
Urine pregnancy	7.4.6.4				X				Only as medically indicated for females of childbearing potential.

Table 10: Table of Required Laboratory Analytes

Serum Chemistries	Serology	Hematology	Coagulation
Albumin	HBsAg	Hemoglobin	PT
Alkaline phosphatase	Anti-HBsAg	Hematocrit	PTT
ALT	Anti-HB core IgG	Platelet count	aPTT
AST	HCV antibody	Red blood cell count	INR
Bicarbonate	HCV-RNA	White blood cell count	
Blood Urea Nitrogen	HBV-DNA	Differential cell count:	
Calcium		Basophils	
Chloride		Eosinophils	
Creatinine		Lymphocytes (absolute)	
Glucose		Monocytes	
LDH		Neutrophils (absolute)	
Phosphate			
Potassium			
Sodium			
Total bilirubin ^a			
Direct bilirubin ^a			
Indirect bilirubin			
Total serum protein			
Total cholesterol			
CRP			

CRP = C-reactive protein.

^a Only required if total bilirubin is elevated.

6.1. Screening

The screening period is the interval between the signing of the ICF and the day that the subject is enrolled in the study (Day 1). Screening may not exceed 28 days. Informed consent must be obtained before performing any study-specific procedures. Assessments that are required to demonstrate eligibility may be performed over the course of 1 or more days during this phase.

Procedures conducted as part of the subject's routine clinical management (eg, blood count, imaging study) and obtained before signing of informed consent may be used for screening or baseline purposes provided that the procedure meets the Protocol-defined criteria and has been performed in the timeframe of the study. Results from the screening visit evaluations will be reviewed to confirm subject eligibility before enrollment or the administration of study drug. Tests with results that fail eligibility requirements may be repeated once during the screening phase if the investigator believes the results to be in error. For screening assessments that are repeated, the most recent available result before enrollment will be used to determine subject eligibility. Treatment should start as soon as possible, but within 2 days after the date of enrollment. Additionally, a subject who fails screening may repeat the screening process 1 time if the investigator believes there has been a change in eligibility status (eg, following recovery from an infection).

6.2. Treatment

The treatment period begins on the day that the subject receives the first dose of study drug (Day 1). This day must be no more than 28 days after the subject has signed the ICF. Dates for subsequent study visits will be determined based on this day and should occur within the visit windows outlined in the schedule of assessments ([Table 8](#)) unless delayed for safety reasons.

6.3. End of Treatment

There is no predefined EOT. If a decision is made that the subject will permanently discontinue study treatment, then the EOT visit should be conducted. If the EOT visit coincides with a regular study visit, then the EOT evaluations will supersede those of that scheduled visit, and the data should be entered in the EOT page in the eCRF. The subject should be encouraged to return for follow-up visits.

6.4. Follow-Up

6.4.1. Safety Follow-Up

The safety follow-up period is the interval between the EOT visit and the scheduled follow-up visit, which should occur 30 to 35 days after the EOT visit (or after the last dose of study drug if the EOT visit was not performed). Adverse events and SAEs must be reported up until at least 30 days after the last dose of study drug, the date of the follow-up visit, or until toxicities resolve, return to baseline, or are deemed irreversible, whichever is longer. Reasonable effort should be made to have the subject return for the follow-up visit and report any AEs that may occur during this phase.

If a subject is scheduled to begin a new anticancer therapy before the end of the safety follow-up period, the safety follow-up visit should be performed before new anticancer therapy is started.

6.4.2. Disease Status Follow-Up

Subjects who discontinue study treatment for a reason other than disease progression will move into the disease status follow-up period and should be assessed per standard of care to monitor disease status. Every effort should be made to collect information regarding disease status until:

- The start of new antineoplastic therapy.
- Disease progression.
- Death.
- The end of the study.

6.5. Unscheduled Visits

Unscheduled visits may be held at any time at the investigator's discretion, and appropriate clinical and laboratory measurements performed based on AEs or other findings.

7. CONDUCT OF STUDY ASSESSMENTS AND PROCEDURES

7.1. Administration of Informed Consent Form

Valid informed consent must be obtained from the study subject before conducting any study-specific procedures using an ICF approved by the local IRB/IEC that contains all elements required by ICH E6 and describes the nature, scope, and possible consequences of the study in a form understandable to the study subject. Local and institutional guidelines for ICF content and administration must be followed; the original signed ICF must be retained by the investigator, and a copy of the signed ICF must be provided to the study subject. The informed consent process for each subject must be documented in writing within the subject source documentation.

7.2. Interactive Response Technology Procedure

The IVRS will be contacted to obtain a subject ID number when a subject enters screening. Upon determining that the subject is eligible for study entry, the IVRS will be contacted to obtain treatment assignment. Additionally, the IVRS will be contacted during visits when study drug is resupplied.

7.3. Demography and History

7.3.1. Demographics, Medical History, Disease History

Demographic data and a complete medical and medication history, including date of diagnosis of DLBCL, histology, current staging, sites of disease, prior surgery, radiation, and other details related to the disease under study, will be collected at screening.

7.3.2. Prior and Concomitant Medications and Procedures

Prior and concomitant medications and procedures will be reviewed to determine study eligibility. All concomitant medications and measures must be recorded in the eCRF, and any medication received or procedure performed within 30 days before enrollment and up to the safety follow-up visit will be recorded in the eCRF. The medication record will be maintained after signing the ICF to document concomitant medications, including any changes to the dose or regimen. Concomitant medications include any prescription, over-the-counter, or natural/herbal preparations taken or administered during the study period. Concomitant treatments and/or procedures that are required to manage a subject's medical condition during the study will also be recorded in the eCRF.

7.4. Safety Assessments

7.4.1. Adverse Events

Adverse events will be monitored from the time the subject signs the ICF through the safety follow-up. Subjects will be instructed to report all AEs during the study and will be assessed for the occurrence of AEs throughout the study. In order to avoid bias in eliciting AEs, subjects will be asked general, nonleading questions such as "How are you feeling?" All AEs (serious and nonserious) must be recorded on the source documents and eCRFs regardless of the assumption

of a causal relationship with the study drug. The definition, reporting, and recording requirements for AEs are described in Section 8.

7.4.2. Comprehensive Physical Examination

Physical examinations must be performed by a medically qualified individual, such as a licensed physician, physician's assistant, or an advanced registered nurse practitioner, as local law permits.

The comprehensive physical examination will include the following organ or body system assessments: skin; head, eyes, ears, nose, and throat; thyroid; lungs; cardiovascular system; abdomen (liver, spleen); extremities; lymph nodes; a brief neurological examination (eg, reflexes, strength, Romberg's test, vibration sense, and gross sensory perception); and body weight (within 1 lb or 0.5 kg). The initial comprehensive physical examination should include an accurate measurement of the subject's height.

7.4.3. Targeted Physical Examination

A targeted physical examination will be a symptom-directed evaluation conducted by the investigator or designee. The targeted physical examination will include assessment(s) of the body systems or organs, as indicated by subject symptoms, AEs, subject's weight, or other findings.

7.4.4. Vital Signs

Vital sign measurements (blood pressure, pulse, respiratory rate, and body temperature) will be taken with the subject in the recumbent, semirecumbent, or sitting position after 5 minutes of rest. Clinically notable abnormalities that are considered clinically significant in the judgment of the investigator are to be reported as AEs.

7.4.5. Twelve-Lead Electrocardiograms

All 12-lead ECGs will be performed with the subject in a recumbent or semirecumbent position after 5 minutes of rest. Triplicate ECGs will be performed during screening and on Day 1 before starting study treatment. Triplicate ECGs will be performed predose and 2 hours (\pm 15 minutes) after receiving INCB039110 on Day 8. When triplicate ECGs are being obtained, individual measurements should be performed 5 ± 3 minutes apart.

All 12-lead ECGs obtained at subsequent timepoints will be compared with the baseline 12-lead ECGs as follows:

- For ECG morphology, all postdose ECG recordings will be compared with Day 1 predose ECGs.
- For the calculation of changes in cardiac intervals (eg, QT interval), the intervals from the screening and Day 1 predose (triplicate) ECGs will be computed and averaged and used as the baseline for comparison of all postdose intervals.

The investigator or another appropriately trained individual will perform the initial ECG analysis of the data collected for each subject. Electrocardiogram data will be reviewed as necessary by a qualified cardiologist at the study site. If a pattern of abnormalities is observed, the sponsor

reserves the right to have copies (electronic or hard) of any and all ECGs sent to a central ECG laboratory for review.

Electrocardiograms that are identified as abnormal and clinically meaningful compared with the screening assessment should be reported as AEs. For such AEs, the findings of the abnormal ECGs and the corresponding baseline ECG findings must be reported in the eCRF, and copies of the abnormal tracings and corresponding baseline tracings will also be sent to the sponsor and/or sponsor's designee as indicated in the study manual.

Additional ECGs may be performed at the investigator's discretion as clinically indicated.

7.4.6. Laboratory Assessments

Blood draws for laboratory assessments will occur at study visits indicated in [Table 9](#). Blood draws will be completed before the subject receives the morning dose of INCB039110. Specific laboratory assessments are listed in [Table 10](#). The screening portion of the study will require a maximum of 16 mL of blood, the first 28 days on study will require a maximum of 35 mL of blood, and each subsequent 28 days on study will require a maximum of 11 mL of blood for local safety laboratory assessments.

All laboratory assessments will be performed at a local laboratory using institutional best practices. Results and normal reference ranges will be entered into the eCRF.

7.4.6.1. Chemistry

All chemistry and coagulation panel assessments will be performed from blood samples collected using institutional best practices before administration of INCB039110. Results and normal reference ranges will be entered to the eCRF.

7.4.6.2. Hematology

Hematology assessments, including complete blood count with differential, will be performed at a local (site) laboratory using institutional best practices before administration of INCB039110. Results and normal reference ranges will be entered to the eCRF.

7.4.6.3. Urinalysis

Not applicable.

7.4.6.4. Pregnancy Testing

A serum pregnancy test will be performed at screening and EOT. Urine pregnancy test will be performed only if pregnancy is suspected during treatment; positive results must be confirmed with a serum pregnancy test. Pregnancy testing will only be required for women of childbearing potential.

7.4.6.5. Serology

Serology will be performed by local laboratory using institutional best practices on samples drawn at the screening visit.

7.5. Efficacy Assessments

Subjects will have an objective assessment of disease status using PET and diagnostic-quality computed tomography (CT) scan or MRI.

7.5.1. Computed Tomography Scan or Magnetic Resonance Imaging

Subjects will undergo a diagnostic-quality CT or MRI to evaluate measurable disease during the screening phase. If CT/MRI assessment was performed as standard of care before signing of the ICF but within 28 days of Day 1, the results from that assessment may be recorded in the eCRF in lieu of a study-specific assessment.

On-treatment assessments should be repeated at Week 8, Week 16, and every 16 weeks thereafter.

This assessment schedule also applies to those subjects who discontinue study treatment for reasons other than disease progression until disease progression, start of new anticancer therapy, withdrawal of consent, end of the study, or death, whichever occurs first. Scheduled assessments should always be calculated from the first dose of study treatment. Imaging should not be delayed for delays in treatment.

7.5.2. FDG-PET or Combined PET-CT

Positron emission tomography (PET) using [¹⁸F] fluorodeoxyglucose (FDG), or combined PET-CT is required to evaluate disease burden during the screening phase. If FDG-PET assessment was performed as standard of care before signing of the ICF but within 28 days of Day 1, then the results from that assessment may be recorded in the eCRF in lieu of a study-specific assessment.

Subsequently, FDG-PET or PET-CT will be repeated in order to confirm response assessments of CR or if clinically indicated.

This assessment schedule also applies to those subjects who discontinue study treatment for reasons other than disease progression until disease progression, start of new anticancer therapy, withdrawal of consent, end of the study, or death, whichever occurs first. Scheduled assessments should always be calculated from the first dose of study treatment. Imaging should not be delayed for delays in treatment.

7.5.3. Bone Marrow Examination

Bone marrow examination is required as a screening assessment unless performed as per standard of care within 60 days of Day 1. Otherwise, a bone marrow biopsy will be performed only to confirm CR or as clinically indicated. The pathology report result from the bone marrow examination will be captured in the eCRF.

7.5.4. Response Criteria – the Lugano Classification

The Lugano Classification ([Cheson et al 2014](#)) will be used to assess response to treatment (see [Table 11](#)). As PET assessment is required to confirm CR or PR, PET-based response should be applied in most circumstances. Computed tomography/MRI-based response criteria are provided in the event that PET scans cannot be interpreted.

Table 11: Lugano Classification for Response Assessment

Site	PET-Based Response	CT-Based Response
	Complete metabolic response	Complete radiologic response (all of the following)
Lymph nodes and extralymphatic sites	Score 1, 2, or 3 with or without a residual mass on 5PS. ^a	Target nodes/nodal masses must regress to ≤ 1.5 cm in LDi.
Nonmeasured lesion	Not applicable.	Absent.
Organ enlargement	Not applicable.	Regress to normal.
New lesions	None.	None.
Bone marrow	No evidence of FDG-avid disease in marrow.	Normal by morphology; if indeterminate, IHC negative.
	Partial metabolic response	Partial remission (all of the following)
Lymph nodes and extralymphatic sites	
 • Score 4 or 5^a with reduced uptake compared with baseline and residual mass(es) of any size. • At interim, these findings suggest responding disease. • At EOT, these findings suggest residual disease. 	
 • ≥ 50% decrease in SPD of up to 6 target measurable nodes and extranodal sites. • When a lesion is too small to measure on CT, assign 5 mm × 5 mm as the default. • When no longer visible, 0 × 0 mm. 
For a node > 5 mm × 5 mm but smaller than normal, use actual measurement.

Nonmeasured lesions	Not applicable.	Absent/regressed, but no increase.
Organ enlargement	Not applicable.	Spleen must have regressed by > 50% in length beyond normal.
New lesions	None.	None.
Bone marrow	Residual uptake higher than uptake in normal marrow but reduced compared with baseline (diffuse uptake compatible with reactive changes from chemotherapy allowed). If there are persistent focal changes in the marrow in the context of a nodal response, consider further evaluation with MRI or biopsy.	Not applicable.

Table 11: Lugano Classification for Response Assessment (Continued)

Site	PET-Based Response	CT-Based Response
	No metabolic response	Stable disease
Target nodes/nodal masses, extranodal lesions	Score of 4 or 5 ^a with no significant change in FDG uptake from baseline at interim or EOT.	< 50% decrease from baseline in SPD of up to 6 dominant, measurable nodes and extranodal sites; no criteria for progressive disease are met.
Nonmeasured lesions	Not applicable.	No increase consistent with progression.
Organ enlargement	Not applicable.	No increase consistent with progression.
New lesions	None.	None.
Bone marrow	No change from baseline.	Not applicable.
	Progressive metabolic disease	Progressive disease (requires at least 1 of the following)
Individual target nodes/nodal lesions	
Individual target nodes/nodal lesions:
 
 Score 4 or 5a with an increase in intensity of uptake from baseline and/or New FDG-avid foci consistent with lymphoma at interim or EOT assessment. 
Extranodal lesions:
 
 New FDG-avid foci consistent with lymphoma at interim or EOT assessment. 
New lesions:
 
 New FDG-avid foci consistent with lymphoma rather than another etiology (eg, infection, inflammation). If uncertain regarding etiology of new lesions, biopsy or interval scan may be considered. 
Bone marrow:
 
 New or recurrent FDG-avid foci. 	
PPD progression:
 
 An individual node/lesion must be abnormal with all of the following: 
 LDi > 1.5 cm. Increase by ≥ 50% from PPD nadir. Increase in LDi or SDi from nadir: 
 0.5 cm for lesions ≤ 2 cm. 1.0 cm for lesions > 2 cm. In the setting of splenomegaly, the splenic length must increase by > 50% of the extent of its prior increase beyond baseline (eg, a 15 cm spleen must increase to > 16 cm). If no prior splenomegaly, must increase by at least 2 cm from baseline. New or recurrent splenomegaly. New or clear progression of preexisting nonmeasured lesions. Regrowth of any previously resolved lesions. A new node > 1.5 cm in any axis. A new extranodal site > 1.0 cm in any axis; if < 1.0 cm in any axis, its presence must be unequivocal and must be attributable to lymphoma. Assessable disease of any size unequivocally attributable to lymphoma. New or recurrent involvement of the bone marrow

LDi = longest transverse diameter of lesion; PPD = cross product of the LDi and perpendicular diameter; SDi = shortest axis perpendicular to the LDi; SPD = sum of the product of the perpendicular diameters for multiple lesions.

^a PET 5-point scale: 1) no uptake above background; 2) uptake ≤ mediastinum; 3) uptake > mediastinum but ≤ liver; 4) uptake moderately > liver; 5) uptake markedly higher than liver and/or new lesions; X) new areas of uptake unlikely to be related to lymphoma.

[figure not shown]

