3.1. Subject Inclusion Criteria

The following criteria are required for inclusion in the study:

1. Male or female, 18 years of age or older.
2. Histologically documented diagnosis of *de novo* DLBCL.
 - a. For Phase 1, subjects may have any DLBCL subtype.
 - b. For Phase 2, subjects must have ABC or unclassifiable subtypes of DLBCL confirmed by immunohistochemistry (IHC) using the Hans algorithm.

Subjects having a computed tomography (CT) scan abnormality with uncertain interpretation following completion of the most recent treatment regimen must have biopsy confirmation of residual DLBCL before study entry.

3. Relapsed or refractory DLBCL, defined as having received at least 1 but no more than 3 prior treatment regimens and ineligible for HDC/ASCT.
4. Fluorodeoxyglucose-avid disease (based on local evaluation) per the Lugano Classification ([Cheson et al 2014](#)). Fluorodeoxyglucose-avid disease is defined as disease with a 5-point scale (5PS) score of 4 or 5.
5. Subjects must have archived tumor tissue (block or 15-20 unstained slides) available, or be willing to undergo an incisional or excisional lymph node biopsy of accessible adenopathy (or, in less accessible lymph nodes, 4 to 8 core biopsies).
6. At least 1 measurable (≥ 2 cm in longest dimension) lesion on CT scan or magnetic resonance imaging (MRI).
7. Eastern Cooperative Oncology Group (ECOG) performance status 0 to 2.
8. Adequate bone marrow, renal, and hepatic function, per local reference laboratory ranges (values must not be achieved with growth factors) as follows:
 - a. ANC $\geq 1.5 \times 10^9/L$.
 - b. Platelet count $\geq 75 \times 10^9/L$.
 - c. Hemoglobin ≥ 8.0 g/dL (transfusions are permitted to achieve required hemoglobin level).
 - d. Serum creatinine ≤ 2.0 g/dL or measured or calculated creatinine clearance ≥ 30 mL/min by the Cockcroft-Gault Equation.

- e. Aspartate aminotransferase (AST) and ALT $\leq 2.5 \times$ institutional upper limit of normal (ULN) or $\leq 5 \times$ ULN for subjects with known hepatic metastases.
 - f. Total bilirubin $\leq 1.5 \times$ ULN if no liver metastases or $< 3 \times$ ULN in the presence of liver metastases or presence of documented Gilbert's syndrome (unconjugated hyperbilirubinemia). Further evaluation should be performed to confirm and document the origin of increase.
9. Prothrombin time (PT)/international normalized ratio (INR) $< 1.5 \times$ ULN and activated partial thromboplastin time (aPTT) $< 1.5 \times$ ULN.

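### In Table 11 the CT-based complete response rule sets no condition for a measured extranodal lesion, so when PET cannot be read a subject with a persisting extranodal mass can count as a responder

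*Protocol*

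**What the plan says.** Protocol Section 7.5.4 directs assessors to Table 11 for response. PET-based criteria are the default, and the CT/MRI column is supplied for PET scans that cannot be interpreted.

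The CT-based CR block is conjunctive: "Complete radiologic response (all of the following". Its rows are:

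- **Lymph nodes and extralymphatic sites:** "Target nodes/nodal masses must regress to ≤ 1.5 cm in LDi"
- **Nonmeasured lesions:** absent
- **Organ enlargement:** back to normal
- **New lesions:** none
- **Bone marrow:** normal by morphology, or IHC negative if indeterminate

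For the same row, the CT-based PR cell reads "≥ 50% decrease in SPD of up to 6 target measurable nodes and extranodal sites". The stable disease cell is a smaller "decrease from baseline in SPD of up to 6 dominant, measurable nodes and extranodal sites", with no progression. The row label in the stable disease block lists extranodal lesions as an item separate from target nodes and nodal masses.

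Inclusion criterion 6 (Section 3.1) asks for one measurable lesion of at least 2 cm and does not require it to be nodal. Under protocol Section 9.4.1 a responder is anyone with a best overall response of PR or better. SAP Section 7.3.1 takes the highest postbaseline response. The SAP cites the Lugano Classification and does not restate its criteria.

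**The concern.** The CR cell is narrower than its own row label and narrower than the PR and stable disease cells in the same column. A measured extranodal mass enters the size sum for PR and stable disease but has no bearing on CR. A subject whose nodes shrink below the limit while an extranodal mass persists can meet all the CR conditions. A subject with only extranodal target disease meets the nodal condition by default.

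One such grade is enough to make a responder. It then counts toward the Stage 1 rule (10 or more of 22), the success rule (29 or more of 60), the ORR estimate and its interval, and the duration and durable response analyses, which are built on responders. Response is assessed by the investigator (the planned SAP listing is of investigator response). The sections reviewed describe no central reading, so the wording of the table is the main control.

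**Working it through.** **1. Which CT-based CR row could reach a measured extranodal mass?**

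| CT-based CR row | Reaches a measured extranodal mass? |
|---|---|
| Nodes and extralymphatic sites | No; the cell names nodes and nodal masses only |
| Nonmeasured lesions | No; the mass is measured |
| Organ enlargement | No, if the mass is in soft tissue or in an organ that is not enlarged |
| New lesions | No; present at baseline |
| Bone marrow | No |

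**2. Worked case (sizes are illustrative).** Assume no nonmeasured or new lesions, no organ enlargement, and normal marrow.

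| Lesion | Baseline (cm) | Follow-up (cm) | Area (cm²) |
|---|---|---|---|
| Node | 2.0 × 1.6 | 1.4 × 1.2 | 3.20 → 1.68 |
| Extranodal mass | 5.0 × 4.0 | 4.5 × 3.5 | 20.00 → 15.75 |
| Sum (SPD) | | | 23.20 → 17.43 |

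Change = (17.43 − 23.20) / 23.20 = −24.9%.

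- PR needs a decrease of at least 50%: not met.
- Stable disease (decrease under 50%, no progression): met.
- CR: the node is 1.4 cm, within the 1.5 cm limit, and every other row is satisfied, so it is met.

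The same scan is both stable disease and CR. With the extranodal mass alone, the change is (15.75 − 20.00) / 20.00 = −21.3%, and the nodal condition is met because there is no node to fail it.

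**3. The plan's design, reproduced.** Inputs from protocol Sections 4.1.2, 9.2.2 and 9.4.1: stop if 9 or fewer of 22 respond, otherwise add 38, success if 29 or more of 60, p0 = 0.40, p1 = 0.55.

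P(success | p) = Σ over x = 10 to 22 of P(X1 = x | 22, p) × P(X2 ≥ 29 − x | 38, p)

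- p = 0.40: 0.0949 (planned at most 0.10)
- p = 0.55: 0.8004 (planned 0.80)

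The stated design is correct.

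**4. Effect of misgrading on type I error.** Let m be the share of true nonresponders graded CR through the gap. With a true rate of 40%, the observed rate is p = 0.40 + 0.60 × m. The documents give no value for m, so this is a range of assumptions.

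| m | p | P(success) |
|---|---|---|
| 0 | 0.4000 | 0.0949 |
| 0.25% | 0.4015 | 0.0988 |
| 0.5% | 0.4030 | 0.1029 |
| 1% | 0.4060 | 0.1114 |
| 2% | 0.4120 | 0.1297 |

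The planned 0.10 is crossed between m = 0.25% and m = 0.5%.

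**The case against.** The strongest reply is that PET largely closes the gap. Section 7.5.4 requires PET to confirm CR or PR and applies PET-based response in most circumstances. Section 7.5.2 and Table 8 also call for PET to confirm CR, and inclusion criterion 4 admits only FDG-avid disease. A persisting mass with unchanged uptake would be graded as no metabolic response. A CT-based CR on a scheduled scan is then a trigger for confirmation and not yet a counted response. This stands, and it limits the point to subjects whose PET cannot be interpreted. Within that group the gap also needs a measured extranodal target, nodes within the limit, clean remaining rows, and an investigator willing to call the result complete. It does not remove the point, since the CT column exists for the cases in which PET cannot correct the grade.

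A second reply is that the governing criterion is the cited classification and that a sensible assessor would not ignore extralymphatic disease. That may be so, but the protocol sends assessors to Table 11, and two assessors could grade the same scan differently. The source is not available here, so whether the line was lost in transcription cannot be settled.

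A third is that the line was lost when the PDF was read. This cannot be excluded. However, the cell is a complete sentence and the rows after it are intact.

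A reader might also infer that a CR which does not satisfy PR is itself proof of error. It is not. The node in the worked case, taken alone, goes from 3.20 to 1.68 cm² (−47.5%). It meets the absolute nodal limit while missing the 50% rule. The error lies in the missing extranodal condition and not in the lack of nesting.

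**Conclusion.** The point holds on the text. The CT-based CR rule omits measured extralymphatic lesions, and when the CT column decides it can turn stable disease into a counted response. It is a wrong rule in a fallback column, with narrow reach. The sample size, power and decision rules are unaffected.

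If 0.25% to 2% of true nonresponders were misgraded, type I error would move from 0.095 to between 0.099 and 0.130. This range is an assumption and not a forecast.

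A reader might go further and suppose one or two false responders in 60, which would give 0.145 or 0.210. With 36 true nonresponders expected under the null (0.60 × 60), that means misgrading 1/36 = 2.8% or 2/36 = 5.6% of them. Nothing in the documents supports rates that high, given the PET requirement.

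**What to change.** Check the CT-based CR cell of Table 11 against the cited classification and add the condition that no measured extralymphatic disease remains. The table already codes a lesion that is no longer visible as 0 × 0 mm, so the data convention exists. Use the same wording in the response derivation that supports SAP Section 7.3.1.

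Do not instead require that a CT-based CR also satisfy the CT-based PR rule. That would regrade genuine complete responses of small nodes, such as the −47.5% node above, as stable disease.

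The cost is one line in the table and one in the derivation. No scans, subjects or design figures change. Any CT-based CR with residual measured extranodal disease would become PR or stable disease according to its SPD.
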